### 7.1.2. Qualification Phase

## 7.1.2.1. Day -10 to Day -1

During the Qualification Phase, subjects will be admitted to a CRU for a stabilization period starting on Day -10 during which all subjects will be stabilized on a short-acting oral opioid (i.e., morphine) to suppress opioid withdrawal. Subjects will receive IR morphine 30 mg, QID for a total daily dose of 120 mg; subjects will be permitted to receive an additional dose of IR morphine 30 mg dose (total daily dose of 150 mg), as needed (PRN) for the first 3 days only. At inpatient check-in, ancillary medications will be made available for symptomatic relief of withdrawal (see Table 5Error! Reference source not found.Error! Reference source not found. for the list of allowed medications). Subjects will receive IR morphine 30 mg (as outlined above) for a minimum of 3 days and a maximum of 7 days prior to entering the Qualification/Baseline Hydromorphone Challenge Session, dependent on the individual's underlying level of dependence.

During this stabilization period, subjects will be monitored carefully for safety. Before each scheduled IR morphine 30 mg dose is administered, research/nursing staff will record oxygen saturation and respiratory rate and assess the subject for sedation and/or intoxication. If respiratory rate drops to <12 breaths per minute or oxygen saturation is <95%, the measurements will be repeated and recorded. If either oxygen saturation or respiratory rate remains outside the pre-specified parameters or the subject appears sedated or intoxicated, the oral maintenance dose of IR morphine 30 mg will be withheld and a study Investigator notified. The withheld dose may be administered later (and the administration time recorded) once it is determined that the subject's status has returned to within a safe range.

On the evening prior to and on the morning of each Qualification/Baseline Hydromorphone Challenge Session day i.e., Day -3, Day -2 and Day -1, subjects will not receive their IR morphine 30 mg dose; therefore, the last active dose of IR morphine 30 mg will be administered a minimum of 12 hours before administration of hydromorphone during the Hydromorphone Challenge Session (see sample IR morphine 30 mg administration schedule in Section 17.1).

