#### 7.1.4. Hydromorphone Challenge Sessions

Each Hydromorphone Challenge Session in the Qualification Phase and Treatment Phase will consist of the injection of 3 doses of IM hydromorphone 10 mg/mL (0 mg [placebo], 6 mg and 18 mg) administered once daily over 3 consecutive days in randomized order. Subjects will be randomized in a 1:1:1:1:1 ratio to 1 of 6 treatment sequences according to two 3 × 3 William squares. The following treatment sequences will be used: ABC, ACB, BAC, BCA, CAB, and CBA, where A, B, and C are IM Hydromorphone Challenge Sessions with 0 mg (placebo), 6 mg, and 18 mg, respectively. The volume of the 0 mg and 6 mg doses of IM hydromorphone will be the same as the volume of the 18 mg hydromorphone dose. Safety and pharmacodynamic assessments will be performed immediately following each dose of hydromorphone administered on each day of the Hydromorphone Challenge Session for a maximum 5 hours after Hydromorphone Challenge Session. Plasma BPN and norbuprenorphine levels will also be obtained approximately 60 minutes prior to hydromorphone dosing on each day of the Hydromorphone Challenge Sessions. After each dose of hydromorphone, subject's oxygen saturation, respiratory rate, and overall safety profile will be reviewed by the research/nursing staff (as described in Section 7.1.2.1) to determine whether it is safe to proceed with administration of the next dose of hydromorphone.

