# 10.6. Additional Safety Measures and Withdrawal

#### 10.6.1. Opioid Effects

Buprenorphine and hydromorphone can produce the typical side effect profile of mu opioid agonists, and these may include nausea, vomiting, headache, dry mouth, itchiness, drowsiness, sweating, dizziness, stimulation, somnolence, lightheadedness, restlessness, a feeling of well-being, talkativeness, urinary retention and constipation. More serious side effects may include allergic reaction and respiratory depression. However, subjects will be opioid-dependent and, thus, familiar with these common side effects, and not likely to experience the severe side effects such as allergic reaction.

Physiological and behavioral effects, as well as the emergence of possible side effects, will be monitored daily during Hydromorphone Challenge Sessions. Subjects who exhibit hypersensitivity (i.e., experience a SAE) following administration of any of the drugs will be excluded from further research participation. Heart rate, blood pressure, oxygen saturation and respiratory rate will be monitored frequently throughout sessions. However, if a subject experiences an allergic reaction, diphenhydramine will be available for oral administration.

While the risk of significant respiratory depression may be decreased in opioid-dependent individuals (due to greater tolerance), standardized criteria for nursing staff and research personnel will be employed during the monitoring of individuals. If respiratory rate drops below 12 breaths/min accompanied by sedation, subjects will be prompted verbally to breathe. This approach of physical and verbal stimulation is often sufficient to prompt breathing and restore a normal respiratory rate. Subjects will be monitored carefully with a watch-and-wait approach and will be accompanied continuously by nursing personnel and evaluated by the staff physician. If clinical evaluation determines that a subject's level of sedation is increasing, naloxone will be promptly administered parenterally to produce immediate reversal of the hydromorphone effects. Naltrexone will also be available if longer blockade is necessary.

The study will be conducted in CRUs with trained nursing staff available on site. A crash-cart with naloxone will be on site as well. Emergency response will be available by a physician codeteam if needed.

Version: 2.0, 17NOV2015 Page 65 of 99

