#### 12.3.4.1. Adverse Events

Adverse events will be coded by system organ class (SOC) and preferred term using the Medical Dictionary for Regulatory Activities (MedDRA) reporting system. Treatment-emergent AEs are defined as any of the following:

- Non-serious AEs with onset on the date of first dose of treatment with the study drug through discharge or Early Termination, whichever occurs first;
- Serious AEs with onset on the date of first dose of treatment with the study drug through 30 days after discharge or Early Termination, whichever occurs first;
- AEs that start before the start of treatment but increase in severity or relationship at the time of or following the start of treatment through discharge or Early Termination, whichever occurs first.

The number and percentage of subjects with TEAEs will be displayed for each treatment group. During the Qualification Phase subjects TEAEs will be displayed by IR morphine 30 mg

Version: 2.0, 17NOV2015 Page 72 of 99

treatment or by hydromorphone treatment groups i.e., 0 mg 6 mg or 18 mg - on the days of hydromorphone challenges. During the Treatment Phase, TEAEs will be displayed by CAM2038 q1w relevant dose and hydromorphone relevant dose i.e., 0 mg 6 mg or 18 mg - on the days of hydromorphone challenges. TEAEs will be displayed by SOC and preferred term. Additionally, TEAEs will be tabulated for each treatment group by severity and by relationship to the study drug. A listing of SAEs will be provided if applicable.

If an AE is considered to be caused by a drug, the Investigator will note which drug caused the AE.

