4.0 STUDY DESCRIPTION

4.1 STUDY OBJECTIVES

The primary objective of this study is:

- To evaluate the degree of opioid blocking effects of CAM2038 q1w following administration of intramuscular (IM) hydromorphone (6 mg and 18 mg) compared to administration of 0 mg IM hydromorphone (placebo) on subjective opioid effects in subjects with opioid use disorder, as measured by the Drug Liking visual analog scale (VAS).

The secondary objectives of this study are:

- To evaluate the degree of opioid blocking effects of CAM2038 q1w following administration of IM hydromorphone (6 mg and 18 mg) compared to administration of 0 mg IM hydromorphone (placebo) on subjective opioid effects in subjects with opioid use disorder, as determined by the secondary outcome measures.
- To explore the relationship between plasma buprenorphine (BPN) concentration and blockade of the subjective opioid effects of hydromorphone.
- To examine the safety and tolerability of CAM2038 q1w when co-administered with hydromorphone.

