6.1 DEFINITION OF BASELINE

Unless otherwise stated, the last observed measurement prior to or on the date of randomization will be considered the baseline measurement. If multiple observations are made during baseline, the baseline will be defined as average of the observations obtained during the baseline phase.

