11.6 VITAL SIGNS

Vital signs will consist of blood pressure (systolic and diastolic blood pressure, mmHg), pulse rate (beats per minute), and respiratory rate (breaths/min), and oxygen saturation (%) collected while sitting, following a rest period of at least 3 minutes. Vital sign values and change from baseline in the vital signs will be summarized for each treatment group.

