TABLE 14.3.8	Summary of All Adverse Events That Lead to Study Discontinuation by System Organ Class and Preferred Term for CAM2038 Doses and Overall (Safety Population)
TABLE 14.3.9	Summary of All Serious Adverse Events That Lead to Study Discontinuation by System Organ Class and Preferred Term for CAM2038 Doses and Overall (Safety Population)
TABLE 14.3.10	Summary of All Deaths and Hospitalizations for CAM2038 Doses and Overall (Safety Population)
TABLE 14.4	Summary of Columbia Suicide Severity Ratings by CAM2038 Doses and Time

	(Safety Population)
TABLE 14.5	Summary of Montgomery-Asberg Depression Rating by CAM2038 Doses and Time (Safety Population)
TABLE 14.6.1.1	Summary of Clinical Hematology Data by CAM2038 Doses and Time (Safety Population)
TABLE 14.6.1.2	Shift from Baseline in Laboratory Tests: Hematology by CAM2038 Doses (Safety Population)
TABLE 14.6.2.1	Summary of Clinical Chemistry Data by CAM2038 Doses (Safety Population)
TABLE 14.6.2.2	Shift from Baseline in Laboratory Tests: Chemistry by CAM2038 Doses (Safety Population)
TABLE 14.6.3.1	Summary of Clinical Coagulation Profile Data by CAM2038 Doses (Safety Population)
TABLE 14.6.3.2	Shift from Baseline in Laboratory Tests: Coagulation Profile by CAM2038 Doses (Safety Population)
TABLE 14.6.4	Number (%) of Patients with Abnormal Physical Examination Findings by CAM2038 Doses (Safety Population)
TABLE 14.6.5	Summary of Vital Signs by CAM2038 Doses at Each Visit (Safety Population)
TABLE 14.6.6	Summary of 12-Lead ECG Conclusions by CAM2038 Doses (Safety Population)
TABLE 14.6.7	Summary of 12-Lead ECG Individual Parameters by CAM2038 Doses (Safety Population)

List of Listings

Number	Title
LISTING 16.2.1	Patient Meets Inclusion Criteria
LISTING 16.2.2	Eligibility for Randomization
LISTING 16.2.3	Patient Randomization
LISTING 16.2.4.1	Demographics
LISTING 16.2.4.2	Medical History
LISTING 16.2.4.3	Psychiatric History
LISTING 16.2.5.1	CAM2038 Injection
LISTING 16.2.5.2	Injection Site Examination/ Treatment Compliance
LISTING16.2.6.1	COWS, C-SSRS, MADRS, and OOWS Scales
LISTING16.2.6.2	VAS Scales
LISTING16.2.7.1	Adverse Events
LISTING16.2.7.2	Serious Adverse Events
LISTING16.2.7.3	Adverse Events That Lead to Study Drug Discontinuation
LISTING16.2.7.4	Adverse Events That Have Death as the Outcome
LISTING16.2.7.1	Death Report
LISTING16.2.7.1	Prior and Concomitant Medications/Procedures
LISTING16.2.8.1	Lab Test Samples
LISTING16.2.8.2	Clinical Hematology
LISTING16.2.8.3	Clinical Chemistry

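### The only vital-signs table is by CAM2038 dose and visit, so it cannot attribute a respiratory-rate change to hydromorphone 0, 6 or 18 mg

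*SAP*

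**What the plan says.** SAP 4.1 lists among the secondary objectives: "To examine the safety and tolerability of CAM2038 q1w when co-administered with hydromorphone".

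For vital signs, which include respiratory rate, SAP 11.6 says: "Vital sign values and change from baseline in the vital signs will be summarized for each treatment group". On its own this is ambiguous, because SAP 11.2 also speaks of hydromorphone treatment groups. The title of Table 14.6.5 in Appendix A settles it: "Summary of Vital Signs by CAM2038 Doses at Each Visit (Safety Population". It is the only vital-signs table in Appendix A, and no figure shows vital signs. Protocol 12.3.4.3 asks for mean, SD, median, minimum and maximum of values and of changes from baseline, with no split by challenge dose. SAP 6.0 sets the same statistics by default. For the changes, SAP 6.1 fixes the reference: "the last observed measurement prior to or on the date of randomization will be considered the baseline measurement", or an average if there are several baseline observations.

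Within each challenge session the three hydromorphone doses are "administered once daily over 3 consecutive days in randomized order" (protocol 7.1.4). The footnotes to protocol Table 4 schedule vital signs before each challenge dose and up to 5 hours after it.

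Adverse events are treated differently. On challenge days in the Treatment Phase, protocol 12.3.4.1 says "TEAEs will be displayed by CAM2038 q1w relevant dose and hydromorphone relevant dose", and SAP Tables 14.3.3.1.2, 14.3.3.1.3, 14.3.4.1.2 and 14.3.4.1.3 follow that split.

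The protocol uses 12 breaths/min as a monitoring limit. Before each morphine dose: "If respiratory rate drops to <12 breaths per minute or oxygen saturation is <95%, the measurements will be repeated and recorded" (7.1.2.1). Sections 7.1.4 and 10.4.5.2 refer back to that rule for the review after each hydromorphone dose. Section 10.6.1 adds: "If respiratory rate drops below 12 breaths/min accompanied by sedation, subjects will be prompted verbally to breathe".

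**The concern.** Protocol 10.6.1 names respiratory depression among the more serious effects of buprenorphine and hydromorphone. A direct description of co-administration safety is whether respiratory rate falls as the challenge goes from 0 to 6 to 18 mg under CAM2038. The trial randomizes that factor within subject and collects the readings, yet the planned table averages over it. A split by visit does not recover dose, because dose order differs between subjects. The change column does not help either, since its reference is a baseline set before CAM2038 and not the reading taken that morning before hydromorphone. The clinical study report could therefore show mean respiratory rates by CAM2038 group and day that say little about the combination.

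**Working it through.** The plan states no figure to reproduce here, so the check is of the design and of what each planned output can show.

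**Inputs.** 24 completers per CAM2038 group (protocol 12.1); six sequences with equal allocation (protocol 7.1.4, SAP 4.3); four Treatment Phase sessions of three days; challenge-day vital signs before dosing and at 15, 30, 45, 60, 90, 120, 180, 240 and 300 minutes after it (Table 4 footnotes), which is 9 post-dose readings.

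**Dose mix in a row.** 24 / 6 = 4 subjects per sequence. Each dose occupies a given day in 2 of the 6 sequences, so 2 × 4 = 8 subjects are on each of 0, 6 and 18 mg on any challenge day. The 18 mg share of challenge subject-days is the same at every level of pooling:
- day: 8/24 = 1/3
- session: 24/72 = 1/3
- week: 48/144 = 1/3
- Treatment Phase: 96/288 = 1/3

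The result therefore does not depend on whether visit means a day, a session or the stay. If a row also takes in non-challenge days, the share is smaller.

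**Effect on the mean.** Pooled mean shift = (shift at 0 + shift at 6 + shift at 18) / 3. The shifts below are assumed for illustration; the documents give none.

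| 0 mg | 6 mg | 18 mg | pooled |
|---|---|---|---|
| 0 | 0 | −3 | −1.0 |
| 0 | 0 | −6 | −2.0 |
| 0 | −1 | −3 | −1.3 |
| 0 | −1 | −6 | −2.3 |

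**Effect on the other statistics.** The row minimum and maximum are not divided by three. A very low rate, or the largest fall from baseline, appears at full size but without the dose that produced it. The median is not scaled by one third either. For these statistics the loss is attribution, not visibility.

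**What other outputs supply.**
- Oxygen saturation below 95% is recorded as an adverse event (protocol 10.4.7), so it can appear in the tables split by hydromorphone dose.
- SAP 11.2 attributes an event to hydromorphone only if it occurs within one hour of dosing. Of the 9 post-dose times, 4 (15 to 60 minutes) fall inside that hour and 5 (90 to 300 minutes) after it.
- A low respiratory rate has no equivalent rule. It reaches the adverse-event tables only if it is judged reportable under protocol 10.4.1.1.
- Listing 16.2.8.8 holds vital-sign values but tabulates nothing.

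**Size of the missing split.** Each subject receives each dose once per session. A cell of CAM2038 group × hydromorphone dose × session has 24 completers and 24 × 9 = 216 post-dose readings, and one subject is 1/24 = 4.2 percentage points. There are 2 × 3 × 4 = 24 such cells in the Treatment Phase.

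**The case against.** The best defence is that the plan is less bare than it looks. SAP 11.0 says safety variables are presented according to the study drug actually received, and the protocol lists hydromorphone among the investigational products (9.2). SAP 11.2 leaves room for further safety analyses. Desaturation becomes an adverse event by rule and is tabulated by challenge dose. The planned minima and maxima would expose an extreme reading. No vital-sign safety outcome is pre-specified, no formal safety comparison is planned, and the split could be produced later from the listed data.

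Much of this stands, and it limits the point. A reader might infer that every planned statistic shrinks an 18 mg effect to a third; that is true of means only. A reader might also infer that the plan has no respiratory safety output by challenge dose; the saturation rule and the adverse-event tables contradict that, within the one-hour limit. Nor is 12 breaths/min a safety endpoint: it is a monitoring limit, tied to sedation where it triggers prompting.

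What does not stand is that the general wording supplies the table. The specific title of Table 14.6.5 governs, and an open clause commits to no analysis. That the data could be tabulated later is a reason why the change is cheap, not a substitute for planning it.

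**Conclusion.** The point holds as a descriptive gap. The planned vital-signs outputs cannot attribute a respiratory-rate change to hydromorphone 0, 6 or 18 mg, although co-administration safety is a secondary objective and adverse events are already shown by challenge dose. A mean change confined to 18 mg appears at about one third of its size; extremes appear in full but unattributed.

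The exact third assumes balanced sequences among 24 completers. Table 14.6.5 uses the Safety Population, where dropouts and same-sequence replacements will shift the mix and the denominators somewhat. The documents give no rate of low readings, and none is assumed.

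A reader might infer that subjects are less well protected or that the blockade claim is weakened. Neither follows: respiratory rate and saturation are reviewed after every challenge dose, and the primary analysis does not use vital signs. This is an optional improvement that the sponsor could reasonably adopt.

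**What to change.** Add to SAP 11.6 one descriptive Safety Population table for Treatment Phase challenge days, by CAM2038 group, hydromorphone dose actually received (0, 6, 18 mg) and session. For each cell give:
- the lowest post-dose respiratory rate;
- the largest fall from that day's pre-dose value;
- the number and percentage of subjects with any scheduled reading below 12 breaths/min, with subjects given that dose in that session as the denominator.

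A row for two consecutive scheduled readings below 12 is optional. It would limit the weight of isolated readings, but it is not a protocol rule; the protocol repeats the measurement instead. Note under the table that sedation is not part of the count. If the Qualification session is shown alongside, keep it per session so that 9 readings are set against 9 and not against 36. Footnote that subjects were then on IR morphine, withheld for at least 12 hours, had no CAM2038, and were selected for tolerating both hydromorphone doses (protocol 8.3).

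Keep the existing summaries, listing and adverse-event tables. The cost is one SAP paragraph and one table from readings already scheduled, with no new data, test or alpha. The downside is an extra display and some isolated low readings in the count.

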11.7 PHYSICAL EXAM

Number and percent of subjects with abnormal physical exam findings at Screening will be summarized by CAM2038 group and body system for each treatment group and overall. Physical Exam data for each subject will also be presented in a listing.

11.8 12-LEAD ELECTROCARDIOGRAM (ECG)

12-Lead ECGs will be performed at screening and at Week 24 after the subject has been resting in a recumbent/supine position for at least 3 minutes. The ECG variables will include ventricular heart rate and the PR, QRS, QT, QTcB and QTcF intervals. The ECGs will be signed and dated by a medically-qualified individual to confirm review of the ECG and verify whether any abnormalities are clinically significant.

Number and percent of subjects in each ECG finding category (normal, abnormal not clinically significant, and abnormal and clinically significant), will be summarized for each visit by each treatment group and overall. Summary statistics will be presented for the actual value and change for each ECG parameter.

The results will be summarized by CAM2038 group.

11.9 INJECTION SITE EXAMINATION

The injection site will be visually inspected for evidence of erythema, edema, itching, pain, infection, bleeding, abnormal healing and any other abnormalities.

12.0 IDENTIFICATION AND SUMMARY OF PROTOCOL DEVIATIONS

Major protocol deviations from entry criteria and treatment compliance will be summarized as far as they can be extracted from numeric or coded study data.

13.0 DATA QUALITY ASSURANCE

Accurate and reliable data collection will be ensured by verification and cross check of the CRFs against the investigator's records by the study monitor (source document verification) and by the maintenance of a drug-dispensing log by the investigator. Collected data will be entered into a computer database and subject to electronic and manual quality assurance procedures.

14.0 REFERENCES

15.0 APPENDICES

15.1 APPENDIX A - LIST OF TABLES, LISTINGS, AND FIGURES

List of Tables

Number	Title
TABLE 14.1.1.1	Disposition of Randomized Patients (Safety Population)
TABLE 14.1.1.2	Disposition of Randomized Patients (ITT Population)
TABLE 14.1.1.3	Disposition of Randomized Patients (Completer Population)
TABLE 14.1.2	Demographics (Safety Population)
TABLE 14.1.3	Baseline Clinical Characteristics (Safety Population)
TABLE 14.1.4	Summary of Psychiatric History (Safety Population)
TABLE 14.1.5.1	Prior Medications (Safety Population)
TABLE 14.1.5.2	Concomitant Medications (Safety Population)
TABLE 14.1.6	Substance Abuse Treatment History (Safety Population)
TABLE 14.2.1.1a	Analysis Results for Primary Efficacy Variable Emax of Drug Liking VAS for CAM2038 32 mg (Completer Population)
TABLE 14.2.1.1b	Analysis Results for Primary Efficacy Variable Emax of Drug Liking VAS for CAM2038 24 mg (Completer Population)
TABLE 14.2.1.2a	Analysis Results for Primary Efficacy Variable Emax of Drug Liking VAS for CAM2038 32 mg (ITT Population)
TABLE 14.2.1.2b	Analysis Results for Primary Efficacy Variable Emax of Drug Liking VAS for CAM2038 24 mg (ITT Population)
TABLE 14.2.2.1a	Analysis Results for Primary Efficacy Variable Emax of High VAS for CAM2038 32 mg (Completer Population)
TABLE 14.2.2.1b	Analysis Results for Primary Efficacy Variable Emax of High VAS for CAM2038 24 mg (Completer Population)
TABLE 14.2.2.2a	Analysis Results for Primary Efficacy Variable Emax of High VAS for CAM2038 32 mg (ITT Population)
TABLE 14.2.2.2b	Analysis Results for Primary Efficacy Variable Emax of High VAS for CAM2038 24 mg (ITT Population)
TABLE 14.2.3.1a	Analysis Results for Primary Efficacy Variable Emax of Good Effects VAS for CAM2038 32 mg (Completer Population)
TABLE 14.2.3.1b	Analysis Results for Primary Efficacy Variable Emax of Good Effects VAS for CAM2038 24 mg (Completer Population)
TABLE 14.2.3.2a	Analysis Results for Primary Efficacy Variable Emax of Good Effects VAS for CAM2038 32 mg (ITT Population)
TABLE 14.2.3.2a	Analysis Results for Primary Efficacy Variable Emax of Good Effects VAS for CAM2038 24 mg (ITT Population)
TABLE 14.2.4.1a	Analysis Results for Primary Efficacy Variable Emax of Bad Effects VAS for CAM2038 32 mg (Completer Population)
TABLE 14.2.4.1b	Analysis Results for Primary Efficacy Variable Emax of Bad Effects VAS for CAM2038 24 mg (Completer Population)
TABLE 14.2.4.2a	Analysis Results for Primary Efficacy Variable Emax of Bad Effects VAS for CAM2038 32 mg (ITT Population)

TABLE 14.2.4.2b	Analysis Results for Primary Efficacy Variable Emax of Bad Effects VAS for CAM2038 24 mg (ITT Population)
TABLE 14.2.5.1a	Analysis Results for Primary Efficacy Variable Emax of Sedated Effects VAS for CAM2038 32 mg (Completer Population)
TABLE 14.2.5.1b	Analysis Results for Primary Efficacy Variable Emax of Sedated Effects VAS for CAM2038 24 mg (Completer Population)
TABLE 14.2.5.2a	Analysis Results for Primary Efficacy Variable Emax of Sedated Effects VAS for CAM2038 32 mg (ITT Population)
TABLE 14.2.5.2b	Analysis Results for Primary Efficacy Variable Emax of Sedated Effects VAS for CAM2038 24 mg (ITT Population)
TABLE 14.2.6.1a	Analysis Results for Primary Efficacy Variable Emax of Any Effects VAS for CAM2038 32 mg (Completer Population)
TABLE 14.2.6.1b	Analysis Results for Primary Efficacy Variable Emax of Any Effects VAS for CAM2038 24 mg (Completer Population)
TABLE 14.2.6.2a	Analysis Results for Primary Efficacy Variable Emax of Any Effects VAS for CAM2038 32 mg (ITT Population)
TABLE 14.2.6.2b	Analysis Results for Primary Efficacy Variable Emax of Any Effects VAS for CAM2038 24 mg (ITT Population)
TABLE 14.2.7.1a	Analysis Results for Primary Efficacy Variable Emax of Desire to Use VAS for CAM2038 32 mg (Completer Population)
TABLE 14.2.7.1b	Analysis Results for Primary Efficacy Variable Emax of Desire to Use VAS for CAM2038 24 mg (Completer Population)
TABLE 14.2.7.2a	Analysis Results for Primary Efficacy Variable Emax of Desire to Use VAS for CAM2038 32 mg (ITT Population)
TABLE 14.2.7.2b	Analysis Results for Primary Efficacy Variable Emax of Desire to Use VAS for CAM2038 24 mg (ITT Population)
TABLE 14.2.10.1a	Summary of Change from Baseline in Clinical Opiate Withdrawal Scale (COWS) for CAM2038 32 mg (Completer Population)
TABLE 14.2.10.1b	Summary of Change from Baseline in Clinical Opiate Withdrawal Scale (COWS) for CAM2038 24 mg (Completer Population)
TABLE 14.2.10.2a	Summary of Change from Baseline in Clinical Opiate Withdrawal Scale (COWS) for CAM2038 32 mg (ITT Population)
TABLE 14.2.10.2b	Summary of Change from Baseline in Clinical Opiate Withdrawal Scale (COWS) for CAM2038 24 mg (ITT Population)
TABLE 14.2.11.1a	Summary of Change from Baseline in Objective Opioid Withdrawal Scale (OOWS) for CAM2038 32 mg (Completer Population)
TABLE 14.2.11.1b	Summary of Change from Baseline in Objective Opioid Withdrawal Scale (OOWS) for CAM2038 24 mg (Completer Population)
TABLE 14.2.11.2a	Summary of Change from Baseline in Objective Opioid Withdrawal Scale (OOWS) for CAM2038 32 mg (ITT Population)
TABLE 14.2.11.2b	Summary of Change from Baseline in Objective Opioid Withdrawal Scale (OOWS) for CAM2038 24 mg (ITT Population)
TABLE 14.2.12.1a	Summary of BPN and norpuprenorphine Concentrations for CAM2038 32 mg (Completer Population)
TABLE 14.2.12.1b	Summary of BPN and norpuprenorphine Concentrations for CAM2038 24 mg (Completer Population)
TABLE 14.2.12.2a	Summary of PK Parameters for CAM2038 32 mg (Completer Population)

TABLE 14.2.12.2b	Summary of PK Parameters for CAM2038 24 mg (Completer Population)
TABLE 14.3.1	Summary of CAM2038 Exposure (Safety Population)
TABLE 14.3.2	Summary of All Adverse Events by System Organ Class, Preferred Term, and Relationship to Hydromorphone During Qualification Period (Safety Population)
TABLE 14.3.3.1	Summary of All Adverse Events by System Organ Class, Preferred Term, and Intensity for CAM2038 Doses and Overall (Safety Population)
TABLE 14.3.3.1.2	Summary of All Adverse Events by System Organ Class, Preferred Term, and Intensity for Hydromorphone and CAM2038 24 mg (Safety Population)
TABLE 14.3.3.1.3	Summary of All Adverse Events by System Organ Class, Preferred Term, and Intensity for Hydromorphone and CAM2038 32 mg (Safety Population)
TABLE 14.3.4.1.1	Summary of All Adverse Events by System Organ Class, Preferred Term, and Relationship to Study Drug for CAM2038 Doses and Overall (Safety Population)
TABLE 14.3.4.1.2	Summary of All Adverse Events by System Organ Class, Preferred Term, and Relationship to Study Drug for Hydromorphone and CAM2038 24 mg (Safety Population)
TABLE 14.3.4.1.3	Summary of All Adverse Events by System Organ Class, Preferred Term, and Relationship to Study Drug for Hydromorphone and CAM2038 32 mg (Safety Population)
TABLE 14.3.5	Summary of All Suspected to Be Drug Related Adverse Events by System Organ Class and Preferred Term for CAM2038 Doses and Overall (Safety Population)
TABLE 14.3.6	Summary of Most Common (at least 5%) Adverse Events by System Organ Class and Preferred Term for CAM2038 Doses and Overall (Safety Population)
TABLE 14.3.7	Summary of All Serious Adverse Events by System Organ Class and Preferred Term for CAM2038 Doses and Overall (Safety Population)
TABLE 14.3.8	Summary of All Adverse Events That Lead to Study Discontinuation by System Organ Class and Preferred Term for CAM2038 Doses and Overall (Safety Population)
TABLE 14.3.9	Summary of All Serious Adverse Events That Lead to Study Discontinuation by System Organ Class and Preferred Term for CAM2038 Doses and Overall (Safety Population)
TABLE 14.3.10	Summary of All Deaths and Hospitalizations for CAM2038 Doses and Overall (Safety Population)
TABLE 14.4	Summary of Columbia Suicide Severity Ratings by CAM2038 Doses and Time

	(Safety Population)
TABLE 14.5	Summary of Montgomery-Asberg Depression Rating by CAM2038 Doses and Time (Safety Population)
TABLE 14.6.1.1	Summary of Clinical Hematology Data by CAM2038 Doses and Time (Safety Population)
TABLE 14.6.1.2	Shift from Baseline in Laboratory Tests: Hematology by CAM2038 Doses (Safety Population)
TABLE 14.6.2.1	Summary of Clinical Chemistry Data by CAM2038 Doses (Safety Population)
TABLE 14.6.2.2	Shift from Baseline in Laboratory Tests: Chemistry by CAM2038 Doses (Safety Population)
TABLE 14.6.3.1	Summary of Clinical Coagulation Profile Data by CAM2038 Doses (Safety Population)
TABLE 14.6.3.2	Shift from Baseline in Laboratory Tests: Coagulation Profile by CAM2038 Doses (Safety Population)
TABLE 14.6.4	Number (%) of Patients with Abnormal Physical Examination Findings by CAM2038 Doses (Safety Population)
TABLE 14.6.5	Summary of Vital Signs by CAM2038 Doses at Each Visit (Safety Population)
TABLE 14.6.6	Summary of 12-Lead ECG Conclusions by CAM2038 Doses (Safety Population)
TABLE 14.6.7	Summary of 12-Lead ECG Individual Parameters by CAM2038 Doses (Safety Population)

List of Listings

Number	Title
LISTING 16.2.1	Patient Meets Inclusion Criteria
LISTING 16.2.2	Eligibility for Randomization
LISTING 16.2.3	Patient Randomization
LISTING 16.2.4.1	Demographics
LISTING 16.2.4.2	Medical History
LISTING 16.2.4.3	Psychiatric History
LISTING 16.2.5.1	CAM2038 Injection
LISTING 16.2.5.2	Injection Site Examination/ Treatment Compliance
LISTING16.2.6.1	COWS, C-SSRS, MADRS, and OOWS Scales
LISTING16.2.6.2	VAS Scales
LISTING16.2.7.1	Adverse Events
LISTING16.2.7.2	Serious Adverse Events
LISTING16.2.7.3	Adverse Events That Lead to Study Drug Discontinuation
LISTING16.2.7.4	Adverse Events That Have Death as the Outcome
LISTING16.2.7.1	Death Report
LISTING16.2.7.1	Prior and Concomitant Medications/Procedures
LISTING16.2.8.1	Lab Test Samples
LISTING16.2.8.2	Clinical Hematology
LISTING16.2.8.3	Clinical Chemistry
LISTING16.2.8.4	Clinical Coagulation Profile

LISTING16.2.8.5	Urine Collection/Toxicology
LISTING16.2.8.6	Pregnancy Test
LISTING16.2.8.7	Physical Examination
LISTING16.2.8.8	Vital Signs
LISTING16.2.8.9	12-Lead ECG
LISTING16.2.8.10	Patient Disposition
LISTING16.2.8.11	Protocol Deviations
LISTING16.2.8.12	Plasma concentrations
LISTING16.2.8.13	PK Data

List of Figures

Number	Title
Figure 14.1.1.1	Drug Liking VAS Over Time by Challenge Session for CAM2038 32 mg (Completer Population)
Figure 14.1.1.2	Mean Emax of Drug Liking VAS Over Challenge Sessions for CAM2038 32 mg (Completer Population)
Figure 14.1.1.3	Mean Emax of Drug Liking VAS vs Mean CAM2038 Concentration Over Challenge Sessions for CAM2038 32 mg (Completer Population)
Figure 14.1.2.1	Drug Liking VAS Over Time by Challenge Session for CAM2038 24 mg (Completer Population)
Figure 14.1.2.2	Mean Emax of Drug Liking VAS Over Challenge Sessions for CAM2038 24 mg (Completer Population)
Figure 14.1.2.3	Mean Emax of Drug Liking VAS vs Mean CAM2038 Concentration Over Challenge Sessions for CAM2038 24 mg (Completer Population)
Figure 14.1.3a	Mean (\pm MSE) Concentration over Time for CAM2038 32 mg (linear and semi-logarithmic graphs, Completer Population)
Figure 14.1.3b	Mean (\pm MSE) Concentration over Time for CAM2038 24 mg (linear and semi-logarithmic graphs, Completer Population)
Figure 14.1.3c	Individual Concentrations over Time for CAM2038 32 mg (linear and semi-logarithmic graphs, ITT Population)
Figure 14.1.3d	Individual Concentrations over Time for CAM2038 24 mg (linear and semi-logarithmic graphs, ITT Population)

